5.1.2 Unscheduled Visits

All attempts should be made to keep patients on the study schedule. Unscheduled visits may be necessary to repeat testing following abnormal laboratory results or clinical findings (high IOP), for follow-up of AEs, or for any other reason, as warranted.

5.1.3 Adverse Event Information Collection

The investigator (or designee) will record all AEs that occur during the study.

The definition of an AE and SAE, and information on the determination of severity and relationship to treatment are provided in Section 7.

5.2 Safety and Rescue Criteria.

In the opinion of investigator, if the patient is at harm due to the treatment such as high eye IOP or due to control such as worsening of dry eye parameters, rescue medications can be used. To start IOP lowering medication, the IOP should be about 5 points higher than baseline. For additional dry eye medications/treatments the corneal staining should worsen a full severity grade.

5.2.1 Adverse Event

An AE is any untoward medical occurrence in a patient administered a study drug/treatment which may or may not have a causal relationship with the study drug. Therefore, an AE is any unfavorable and unintended sign (including abnormal laboratory finding), symptom, or disease which is temporally associated with the use of a study drug, whether or not considered related to the study drug.

An AE also includes any worsening (i.e. any clinically significant change in frequency and/or intensity) of a pre-existing condition that is temporally associated with the use of the study drug.

All AEs in this study are Physician documented signs or results or exam findings. Local instillation discomfort, burning, stinging, blurred vision, redness etc will not be necessarily queried but documented in response to “how are you feeling” or how are your eyes feeling” questions.

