5. STUDY SCHEDULE OF EVENTS AND VISIT DESCRIPTIONS

5.1 Schedule of Events

Study assessments and procedures are presented by visit in Table 1

Table 1 Schedule of Events

Procedure	Run In* (Day -14 to -7)	Visit 1* (Day 1)	Visit 2 (Day 14)	Visit 3 (Day 28)	Visit 4 (Day 42)	Early Termination
Informed Consent	X	X**				
Inclusion/Exclusion/Demographics	X	X**				
Medical history and concurrent illnesses	X	X**				
Concomitant medications	X	X	X	X	X	X
Pregnancy Test		X			X	X
Log/Dispense Rescue Meds	X	X	X	X	X	
Insert Study Drug/Control		X				
BSCVA		X			X	X
VAS	X	X		X	X	X
Schirmer (W/O anesthesia)	X	X			X	X
OSS (corneal and conjunctival)	X	X	X	X	X	X
IOP	X	X	X	X	X	X
SLE	X	X	X	X	X	X
Dilated Fundus Exam	X	X**			X	X
Rescue med recording	X		X	X	X	X
AE recording		X	X	X	X	X

*If no run-in required, patient will start at baseline visit/ Day 1

**Required in absence of run-in visit

After having obtained an informed consent patients will be assigned a unique patient number and undergo the below procedures in the order they are listed.

1. Medical History and Review of Systems
 - i. Contact lens and glasses wearing (contact lens wear has to be discontinued 1 week prior and for the duration of the study)
 - ii. Current eye drops used:
 - a. Patients who are on dry eye drops, such as artificial tears, cyclosporine, or lifitigrast treatment will be eligible as long as the doses have been stable for at least 3 months
 - b. Patients who are on steroid drops will be placed in a 14 day wash-out period, in both eyes, before they can be eligible. If in the discretion of the principle investigator, discontinuation of the topical treatment could pose any harm to the patient's ocular health, the patient will be excluded.
 - c. Patients who are on anti-histamines, oral (doxycycline or azithromycin) or topical antibiotics (bacitracin or erythromycin ointment) are eligible for as long as the doses have been stable in the past 2 weeks

- d. Patients who are on oral steroids or other anti-inflammatory or immunomodulatory medications are eligible for as long as the doses have been stable in the past 3 months
- e. Patients using glaucoma drops in either eye will be excluded (with the exception of rescue medication)

iii. Current systemic medications (see above)

iv. History of eye diseases and previous eye or eyelid surgery

- a. Patients who had eye surgery in the past 3 months prior to study are ineligible
- b. Patients who had penetrating corneal transplantation are not eligible

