5.1.1 Study Procedures

Patients will be instructed not to instill any eye drops one hour prior to any study visit.

SCREENING VISIT/RUN IN (Day -14 to -7) – Either Examining or Treating physician will perform.

The following information will be collected:

- Informed Consent
- Inclusion/exclusion
- Demographics
- Medical history and concurrent illnesses
- Concomitant medications
- Log/Dispense Rescue medications
- Ocular Surface Disease Index Questionnaire (OSDI)
- Schirmer test without anesthesia
- OSS (Corneal and conjunctival)
- Intraocular Pressure (IOP)
- Slit Lamp Examination (SLE)
- Dilated Fundus Exam (DFE)
- Rescue Med Recording

BASELINE VISIT (Day 1)- Treating Physician (Unmasked)

If run-in Visit was NOT performed:

- Informed Consent
- Inclusion/Exclusion
- Demographics

- Medical History and concurrent illnesses
- Dilated Fundus Exam (DFE)

Needed for all Baseline Day 1:

- Concomitant medications
- Urine Pregnancy Test
- Log/Dispense Rescue Meds
- Insert Study Drug/Control
- Best Corrected Spectacle Visual Acuity (BSCVA)
- VAS
- Schirmer without anesthesia
- OSS
- IOP
- SLE
- AE recording

VISIT 2 (14+/-3 days) – Examining Physician (Masked)

- Concomitant medications
- Log/Dispense Rescue Meds
- OSS
- IOP
- SLE
- Rescue med recording
- AE recording

VISIT 3 (28+/-3 days) – Examining physician (Masked)

- Concomitant medications
- Log/Dispense Rescue Meds
- VAS
- OSS
- IOP
- SLE
- Rescue med recording
- AE recording

VISIT 4 (42+/-3 days) – Examining Physician

- Concomitant Medications
- Log/Dispense Rescue Meds
- Pregnancy Test
- BSCVA
- VAS

- Schirmer W/O anesthesia
- OSS
- IOP
- SLE
- Dilated Fundus Exam
- Rescue med recording
- AE recording

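### Adverse events are tied to study-drug use and recorded only from Day 1, so non-serious harm during the protocol-imposed steroid wash-out is not recorded as an AE

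*Combined protocol and SAP*

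**What the plan says.** **Definition.** Section 5.2.1 opens: "An AE is any untoward medical occurrence in a patient administered a study drug/treatment which may or may not have a causal relationship". It then requires an unfavourable sign, "symptom, or disease which is temporally associated with the use of a study drug, whether or not considered related to the study drug". Clinically significant worsening counts only if it is a worsening "of a pre-existing condition that is temporally associated with the use of the study drug".

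**Schedule.** Section 5.1 places the insert and the sham plug on Day 1. The Table 1 row is "AE recording X X X X X": five marks across six columns, with the run-in cell blank. The 5.1.1 run-in list agrees. It ends with "Rescue Med Recording" and contains no AE item; AE recording first appears in the Day 1 list.

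**Wash-out.** Section 5.1, item 1.ii.b: "Patients who are on steroid drops will be placed in a 14 day wash-out period, in both eyes, before they can be eligible". The next sentence excludes a patient for whom, in the principal investigator's judgement, "discontinuation of the topical treatment could pose any harm" to ocular health. Consent is taken at run-in, and rescue medication is dispensed and recorded there.

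**General statement.** Section 5.1.3: "The investigator (or designee) will record all AEs that occur during the study". It refers to Section 7 for the definitions. Section 7 covers ethics and regulation and contains none, so 5.2.1 is the only AE definition.

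**The concern.** Starting AE collection at dosing is reasonable when nothing is done to patients between consent and dosing. Here something is done: the protocol withdraws a treatment from both eyes. It foresees possible harm by screening out patients judged at risk, and it makes rescue medication available from run-in. It does not provide for recording, as a safety event, harm that occurs despite that screening.

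At stake is the completeness of the record of harm from a required study procedure. The gap matters most for a patient whose eyes deteriorate during wash-out and who is never treated, because that patient has no Day 1 examination to show what happened. The study population is described as patients who require topical steroid treatment, so the wash-out may not be a rare event, although the documents do not say how often it will be needed.

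**Working it through.** The plan gives no figure on this point to reproduce. The check is a reading of the sections side by side, plus one share of days.

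**1. Does a wash-out flare meet the AE definition?** The definition has two conditions: the patient has been administered study drug or treatment, and the event is temporally associated with use of the drug. Before Day 1 neither is met. The clause on pre-existing conditions carries the same drug-use condition, so worsening of dry eye during wash-out does not qualify by that route. The all-AEs statements in 5.1.3 and 5.3 rely on the same definition and do not widen it.

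**2. Is there a scheduled place to record it?** There is none at run-in, in either Table 1 or the 5.1.1 list. Two separate places agree, so this is not a slip in one table or an effect of text extraction. The Early Termination column does have AE recording, but an event in a patient who leaves before insertion would still fall outside 5.2.1.

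**3. What else would pick it up?**

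| Route | What it catches | What it leaves |
|---|---|---|
| Staining, Schirmer, IOP and slit-lamp examination at run-in and Day 1 | Change in each eye | Patients who never attend Day 1; not an AE record |
| Symptom VAS at run-in and Day 1 (Table 1) | Symptom change in each eye | The 5.1.1 run-in list names OSDI, not VAS |
| Rescue and concomitant medication | Treatment of a flare | The separate rescue-recording row is blank at Visit 1, although the log/dispense row is marked |
| SAE question (5.2.2), looking back to the previous visit | Serious events, if asked at Day 1 | Non-serious flares |
| IRB reporting (5.3, 7.4) | Deaths, unanticipated problems, events likely to affect patient safety | Ordinary non-serious flares |

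No row puts a non-serious wash-out flare into the AE record.

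**4. Share of days without scheduled AE recording.** Inputs: run-in window Day -14 to -7 (Table 1) and follow-up of 42 days (synopsis). Count Day -d to Day -1 and Day 1 to Day 42, with no Day 0, at nominal visit days. The share is d / (d + 42).

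- d = 14: 14 / (14 + 42) = 14 / 56 = 25.0%
- d = 7: 7 / (7 + 42) = 7 / 49 = 14.3%

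This applies only to patients who enter through the run-in. Under the Table 1 footnote, other patients start at Day 1. With AE recording from consent, the 7 to 14 days fall to 0. Sample size, power and alpha are unaffected.

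**The case against.** The strongest reply is that the plan is coherent. The definition, Table 1 and the visit lists all start AE collection at treatment, and the safety objective in 2.2 concerns the insert through Day 42. Omitting pre-insertion events is consistent with that objective. The wash-out sentence is also a safeguard, since a patient judged at risk is excluded, and several routes observe the patient before insertion. All of this stands. It limits the point to harm from the wash-out itself, in patients who were not screened out, that is non-serious and so missed by the SAE and IRB routes.

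Three stronger readings are tempting, and the documents do not support them.

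- **A reader might infer that wash-out harm is not recorded at all.** It is not recorded as an AE. The Day 1 examinations of both eyes, the medication logs, the SAE question and IRB reporting each catch part of it.
- **A reader might infer that flares first noted on Day 1 will be charged to the insert or the plug and distort treated versus sham.** Logging such a flare as an AE would mean misapplying 5.2.1. Inclusion criterion 8 requires staining, Schirmer and symptom findings in both eyes on Day 1, and these must precede insertion, so an existing flare is documented at baseline. Wash-out affects both eyes, each patient has one treated and one sham eye, and the allocation is randomised. Pre-insertion events are therefore balanced in expectation. What remains is that no rule asks for an onset date, so a stray pre-insertion event could enter the overall AE count.
- **A reader might want to put a number on the patients or patient-days affected.** The documents do not say how many patients will be on steroid drops at screening, and those off steroids for at least 2 weeks need no wash-out. Any such count would be a guess.

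**Conclusion.** The point holds as a gap in the patient-safety record. Followed exactly, 5.2.1, Table 1 and the 5.1.1 run-in list leave a non-serious wash-out flare out of the AE record, and a patient who deteriorates and never reaches Day 1 contributes no AE. The size is 7 to 14 days per run-in patient, or 14.3% to 25% of nominal on-study days, for a number of patients that the documents do not give. The conclusion assumes that 5.2.1 is applied as written and that the run-in visit falls within its stated window.

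No bias in the treated-versus-sham comparison is expected, and the efficacy analysis is untouched. The change should be made because it is cheap and the study itself imposes the risk, but the trial's main conclusions do not depend on it.

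**What to change.** - In 5.2.1 and 5.2.2, define AEs and SAEs as events from signed consent, whether or not study treatment has been given.
- Add AE recording to the run-in column of Table 1 and to the 5.1.1 run-in list. State that it covers the whole wash-out interval, including for patients who leave before Day 1.
- Record the onset date and the eye for each event, so that events before and after insertion can be told apart.
- Tabulate pre-insertion events separately from post-insertion events, and keep them out of the treated-versus-sham comparison.
- Correct the cross-reference in 5.1.3, which points to a section without the definitions. The 14-day wash-out and the Day -14 to -7 run-in window also disagree and must be reconciled, because together they determine how long the pre-insertion interval is.

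The cost is protocol wording, one more cell in Table 1 and one extra safety table. The reported AE total may rise slightly. No new visit, test or staff is needed, and sample size, power and alpha do not change.

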5.2.2 Serious Adverse Event

A SAE is any untoward medical occurrence that at any dose:

- Results in **death** – includes all deaths, even those that appear to be completely unrelated to study drug (e.g. a car accident in which a patient is a passenger).

- Is **life-threatening** – in the view of the investigator, the patient is at immediate risk of death at the time of the event. This does not include an AE that had it occurred in a more severe form, might have caused death.
- Requires in-patient **hospitalization** or prolongation of existing hospitalization. In-patient hospitalization is defined as admission to a hospital or an emergency room for longer than 24 hours. Prolongation of existing hospitalization is defined as a hospital stay that is longer than was originally anticipated for the event, or is prolonged due to the development of a new AE as determined by the investigator or treating physician.
- Results in persistent or significant **disability/incapacity** (substantial disruption of one's ability to conduct normal life functions).
- Is a **congenital anomaly/birth defect**
- Is an **important medical event** – Important medical events may not be immediately life-threatening or result in death or hospitalization, but may jeopardize the patient or may require intervention to prevent 1 of the other serious outcomes listed above (e.g., intensive treatment in an emergency room or at home for allergic bronchospasm; blood dyscrasias or convulsions that do not result in hospitalization; or development of drug dependency or drug abuse). Any malignancy (other than basal cell skin cancers) would be considered a medically important event.

Serious AEs will be queried by asking “has anything changed in your medical or ocular history since the last visit”.

5.3 Recording and Reporting Adverse Events

All AEs and SAEs will be recorded.

All SAEs, regardless of assessment of causal relationship to study insert will be reported to Ocular Therapeutix.

To report an SAE, Ocular Therapeutix will be contacted at the following:

[**[contact]**](mailto:[contact])

SAE [contact]

The investigator will promptly report to the IRB all unanticipated problems involving risks to patients. This includes death from any cause and all SAEs related to the use of the study insert. All SAEs will be reported to the IRB, regardless of assessed causality.

6. STUDY VARIABLES

6.1 Demographic and Baseline Characteristics

Baseline characteristics will include standard demography (e.g. age, race, etc.), disease characteristics including medical history, and medication history for each patient.

6.2 Primary and Secondary Endpoints

6.3 Primary Objective(s)

To determine the efficacy of dexamethasone insert through Day 28, as measured by –

- Improvement in corneal staining score in the treatment versus sham arm
- Improvement in worst/most bothersome symptom in the treatment versus control group

In addition

- % of patients with improvement of corneal staining score by one severity grade (clinically meaningful) in treatment versus control group
- % of patients with improvement of worst/most bothersome symptom by 30 points (clinically meaningful) in the treatment versus control group

6.4 Secondary Objectives

To determine the safety of dexamethasone insert through Day 42, as measured by –

- Improvement in Schirmer test without anesthesia
- Improvement of conjunctival lissamine green staining score
- Intraocular pressure monitoring
- Cataract Formation
- Adverse Events

7. ETHICAL AND REGULATORY CONSIDERATIONS

7.1 Good Clinical Practice Statement

It is the responsibility of the investigator(s) to ensure that this clinical study will be conducted in accordance with the ethical principles that have their origin in the Declaration of Helsinki, and that are consistent with the ICH guidelines for Good Clinical Practice (GCP) and applicable regulatory requirements.

7.2 Informed Consent

The principles of informed consent are described in ICH Guidelines for GCP. Standard Johns Hopkins Hospital template must be used.

It is the responsibility of the investigator or designee (if acceptable by local regulations) to obtain written informed consent from each patient prior to his/her participation in the study and after the aims, methods, objectives, and potential hazards of the study have been explained to the patient in language that he/she can understand. The informed consent form (ICF) will be signed and dated by the patient and by the investigator or authorized designee who reviewed the ICF with the patient.

Patients who can write but cannot read will have the ICF read to them before signing and dating the ICF.

Patients who can understand but who can neither write nor read will have the ICF read to them in presence of an impartial witness, who will sign and date the ICF to confirm that informed consent was given.

The original ICF will be retained by the investigator as part of the patient's study record, and a copy of the signed ICF will be given to the patient.

If new safety information results in significant changes in the risk/benefit assessment, the ICF will be reviewed and updated appropriately. All study patients will be informed of the new information and provide their written consent if they wish to continue in the study. The original signed revised ICF will be maintained in the patient's study record and a copy will be given to the patient.

7.3 Patient Confidentiality and Data Protection

The investigator will take all appropriate measures to ensure that the anonymity of each study patient will be maintained.

The patient's and investigator's personal data will be treated in compliance with all applicable laws and regulations.

7.4 Institutional Review Board

An appropriately constituted IRB, as described in ICH Guidelines for GCP, will review and approve:

- The protocol, ICF, and any other materials to be provided to the patients (e.g. advertising) before any patient may be enrolled in the study
- Any amendment or modification to the study protocol or ICF before implementation, unless the change is necessary to eliminate an immediate hazard to the patients, in which case the IRB will be informed as soon as possible

Ongoing studies will be reviewed by the IRB/EC on an annual basis or at intervals appropriate to the degree of risk.

In addition, the IRB will be informed of any event likely to affect the safety of patients or the continued conduct of the clinical study.

A copy of the IRB approval letter will be sent to Ocular Therapeutix prior to shipment of drug insert supplies to the investigator. The approval letter will include the study title, the documents reviewed, and the date of the review.

Records of the IRB review and approval of all study documents (including approval of ongoing studies) will be kept on file by the investigator.

REFERENCES

1. Uchino, Miki, and Debra A. Schaumberg. "Dry Eye Disease: Impact on Quality of Life and Vision." *Current Ophthalmology Reports*, vol. 1, no. 2, 2013, pp. 51–57.

Appendix 2: VAS Scales

! '#\$/#&\$ #() *+(\$ --&-(& *\$
\$

Eye Dryness

This questionnaire is in regards to your **current** eye dryness. Please remember to evaluate each eye separately.

Please rate your level of “eye dryness” by placing a vertical mark on the horizontal line on the below scale to indicate the level of dryness.

[figure not shown]
Please think of the feelings of dryness or “stickiness or the need for use of artificial tears BUT NOT sandiness/grittiness, sensitivity to light, redness, or itching.

Zero corresponds to “no dryness” and 100 correspond to “maximal dryness.”

RIGHT EYE:

LEFT EYE:

Eye Discomfort

This questionnaire is in regards to your **current** eye discomfort. Please remember to evaluate each eye separately.

Please rate your level of “eye discomfort” by placing a vertical mark on the horizontal line on the below scale to indicate the level of discomfort.

Please think of pain, stinging, burning, sandiness/grittiness, sensitivity to light, itching, irritation or feeling that something is in the eye.

Zero corresponds to “no discomfort” and 100 correspond to “maximal discomfort.”

Eye Fatigue

This questionnaire is in regards to your **current** eye fatigue. Please remember to evaluate each eye separately.

Please rate your level of “eye fatigue” by placing a vertical mark on the horizontal line on the below scale to indicate the level of fatigue.

Please think of feeling of heaviness in the lids, difficulty keeping eye open, difficulty reading, or just wanting to rest your eyes.

Zero corresponds to “no fatigue” and 100 correspond to “maximal fatigue.”

RIGHT EYE:

LEFT EYE:
